4.2.2 Post-Treatment Period

4.2.2.1 Primary Endpoints for the PTP

Primary endpoints for the PTP will be:

- The proportion of subjects who require retreatment with oral isotretinoin at any time during the PTP; and
- The time at which retreatment is required.

4.2.2.2 Secondary Endpoints for the PTP

Secondary endpoints for the PTP will be:

- The proportion of subjects who require treatment with a prescription anti-acne medication other than oral isotretinoin at any time during the PTP;
- The proportion of subjects who use an over-the-counter (OTC) anti-acne medication at any time during the PTP;
- The severity of acne (lesion count and IGA) at the time of retreatment in subjects treated with a prescription or OTC anti-acne treatment;
- The severity of acne (lesion count and IGA) at each visit;
- The time to retreatment with a prescription or over-the-counter (OTC) anti-acne medication at any time during the PTP;
- The acne-QOL at the end of the PTP;
- Safety as assessed through the monitoring of AEs, laboratory test results, vital signs, and physical examinations.

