Evaluation Criteria:	
The primary endpoint during the ATP will be the change from Baseline to the end of ATP (Week 20/Visit 8) in the acne-specific quality of life (acne-QOL) questionnaire score for those subjects who complete the 20-week ATP and are at least 75% compliant with the treatment regimen.
 
Secondary endpoints for the ATP will be:
 
 • The change from Baseline in the lesion count (nodules and inflammatory lesions) at the end of the ATP;

	
 • The change from Baseline in the acne-QOL score at Weeks 4, 8, 12, and 16 weeks; • The change from Baseline in the IGA at the end of the ATP in subjects who complete the 20-week ATP; • Treatment safety, as determined by the frequency and severity of adverse events (AEs) and local skin irritation. 
Primary endpoints for the PTP will be to determine:
 
 • The proportion of subjects who require retreatment with oral isotretinoin at any time during the PTP; and • The time at which retreatment is required. 
Secondary endpoints for the PTP will be to determine:
 
 • The proportion of subjects who require treatment with a prescription anti-acne medication other than oral isotretinoin at any time during the PTP; • The proportion of subjects who use an over-the-counter (OTC) anti-acne medication at any time during the PTP; • The severity of acne (lesion count and IGA) at the time of retreatment in subjects treated with a prescription or OTC anti-acne treatment; • The severity of acne (lesion count and IGA) at each visit; • The time to retreatment with a prescription or over-the-counter (OTC) anti-acne medication at any time during the PTP; • The acne-QOL at the end of the PTP; • Safety as assessed through the monitoring of AEs, laboratory test results, vital signs, and physical examinations.
Pharmacokinetics Evaluation Criteria:	Not applicable
Safety Evaluation Criteria:	During the ATP: adverse event (AE) incidence and severity, laboratory test results (hematology, serum biochemistry, lipid profile), pregnancy tests, vital signs (systolic and diastolic blood pressure, heart rate, respiratory rate) During the PTP: Serious AEs related to study drug.

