- e. Females of childbearing potential must have a second, confirmatory pregnancy test with negative results that occurs after the 30-day waiting period.
- f. Specified sites will perform photography using equipment supplied by the photography vendor; other sites will use on-site photography equipment.
- g. Only nodules will be counted at Screening.

Table 1-2 Visit Schedule and Assessments – Post-Treatment Phase (PTP)

	Visit 9	Visit 10	Visit 11	Visit 12	Visit 13	Visit 14/EOS
	Week 24 ± 4 days	Week 32 ± 2 weeks	Week 46 ± 2 weeks	Week 72 ± 2 weeks	Week 98 ± 2 weeks	Week 124 ± 2 weeks
Vital signs and weight	X					
Clinical laboratory assessment ^a	X					
Serum chemistry						
Pregnancy test	X					
Prior and concomitant medication assessment	X	X	X	X	X	X
Photography ^b		X	X	X	X	X
Quality of Life Questionnaire		X	X	X	X	X
Investigator's Global Assessment (IGA)		X	X	X	X	X
Lesion count (nodules and inflammatory lesions)		X	X	X	X	X
Adverse event assessment ^c	X	X	X	X	X	X

a. Laboratory assessments at Visit 9 will include fasting clinical chemistry and fasting lipid profile.

b. Specified sites will perform photography using equipment supplied by the photography vendor; other sites will use on-site photography equipment.

c. Only serious adverse events related to study treatment will be collected.

TABLE OF CONTENTS

1.0	SYNOPSIS	2
TABLE OF CONTENTS		7
LIST OF TABLES		11
LIST OF FIGURES		11
LIST OF ABBREVIATIONS AND DEFINITION OF TERMS		12
2.0	INTRODUCTION	14
2.1	Background	14
2.2	Rationale of the Study	15
2.3	Benefit-Risk Assessment	15
3.0	TRIAL OBJECTIVES AND PURPOSE	16
3.1	20-Week Active Treatment Period (ATP)	16
3.2	104-Week Post-Treatment Period (PTP)	17
4.0	STUDY DESIGN	17
4.1	Overall Study Design	17
4.2	Study Endpoints	18
4.2.1	Active Treatment Period	18
4.2.1.1	Primary Endpoint for the ATP	18
4.2.1.2	Secondary Endpoints for the ATP	19
4.2.2	Post-Treatment Period	19
4.2.2.1	Primary Endpoints for the PTP	19
4.2.2.2	Secondary Endpoints for the PTP	19
5.0	SELECTION OF STUDY POPULATION	20
5.1	Subject Population	20
5.2	Inclusion Criteria	20
5.2.1	General Inclusion Criteria	20
5.2.2	Specific Inclusion Criteria	20
5.3	Exclusion Criteria	21
5.3.1	General Exclusion Criteria	21
5.3.2	Female Specific Exclusion Criteria	21
5.3.3	Concurrent Disease Exclusion Criteria	22
5.3.4	Hypersensitivity/Allergy Exclusion Criteria	22
5.3.5	Prohibited Medication Before and/or During the Study	22

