4.0 STUDY DESIGN

4.1 Overall Study Design

This is a single-arm, open-label study consisting of 2 phases: a 20-week (5-month) open-label ATP and a 104-week (2-year) PTP. The total study duration is to be 124 weeks, excluding a screening period. During the ATP, after a Week 2 visit, visits will be scheduled at 4-week intervals for a total of 8 visits (1 screening visit, 1 baseline visit, and 6 on-study visits). During the PTP, the first visit will be 4 weeks after End of Treatment (EOT), the second visit will be 12 weeks after EOT, and subsequent visits will be scheduled at 26-week (\pm 2 weeks) intervals for a total of 6 visits.

Subjects will provide written informed consent, including mandatory photographic consent, on an informed consent form (ICF). Subjects who are under the age of 18 years will sign an assent form and their parent or guardian will sign the ICF. Subjects will then undergo a complete physical examination and will provide blood samples for hematology and fasting clinical chemistry, including liver function tests and a lipid profile with triglyceride levels. Female subjects of childbearing potential will be required to comply with mandatory pregnancy testing (see [Section 7.4.5](#)) and contraception specifications (see [Section 6.6](#)) before receiving study medication.

Subjects who meet the entry criteria will enter a 20-week ATP, during which they will receive Absorica® (isotretinoin) capsules. Dosing will be at an initial titration dose of approximately 0.5 mg/kg/day divided into 2 daily doses for the first 4 weeks, followed by 16 weeks of dosing with approximately 1 mg/kg/day divided into 2 daily doses. Study medication is to be taken

[figure not shown]
without food (ie, 1 hour before or at least 2 hours after the ingestion of food or beverages other than water).

Beginning at Visit 2 (Baseline) and continuing throughout the ATP and PTP (excluding Visits 3 and 9), subjects will be asked to complete an acne-specific quality of life (acne-QOL) questionnaire and photographs will be taken of the subject's face. Safety during the ATP will be assessed by adverse event (AE) monitoring and laboratory test results. Efficacy will be assessed by lesion counts (nodules, inflammatory lesions) and an IGA.

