Subjects who are prescribed a second course of treatment Absorica® or any other formulation of isotretinoin during the PTP will be withdrawn from the study after their lesion count and IGA are recorded. Subjects who use OTC or oral non-isotretinoin acne treatment can remain in the study, but their medication use is to be recorded.

The study design is summarized in [Figure 4-1](#).

Figure 4-1 Study Design

Note: EOT = end of treatment; EOS = end of study

a. A mandatory, confirmatory pregnancy test for female subjects of childbearing potential must be conducted according to the iPLEDGE guidelines.

b. Week 2 safety laboratory tests.

c. 4 Week post treatment safety follow-up

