5.0 SELECTION OF STUDY POPULATION

5.1 Subject Population

It is planned to enroll approximately 200 subjects at approximately 20 sites in the US in order to provide approximately 140 subjects who complete the ATP. An individual subject will be allowed to participate in the study one time only. A rationale for the choice of sample size is provided in [Section 8.2](#) of this protocol.

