- Perform a serum pregnancy test for females of childbearing potential. Ensure that female subjects of childbearing potential are using 2 approved method(s) of contraception.

- Take EOT photographs of the subject's face (see [Section 7.2.13](#)).
- Have the subject complete the acne-QOL questionnaire.
- Complete the lesion count and IGA.
- Record any AEs.
- Schedule the next study visit.

7.2.6 Post Treatment Period – Visit 9 (Week 24 ± 4 days 4 weeks post treatment safety visit)

- Review any concomitant medications that affect acne (including all antibiotics) used since the previous study visit.
- Measure vital signs (systolic and diastolic blood pressure, heart rate, and respiratory rate) with subject in a seated position and record weight.
- Obtain blood samples for a laboratory profile including fasting clinical chemistry and a fasting lipid profile.
- Perform a serum pregnancy test for females of childbearing potential and counsel on any continued birth control needs (iPLEDGE does not require birth control to continue for more than 30 days post last dose)
- Record any AEs.
- Schedule the next study visit.

7.2.7 Post Treatment Period – Visits 10 to 14 (Weeks 32, 46, 72, 98, and 124 ± 2 Weeks)

- Review any concomitant medications that affect acne (including all antibiotics) used since the previous study visit.
- Take photographs as specified for the site (see [Section 7.2.13](#)).
- Have the subject complete the acne-QOL questionnaire.
- Complete the lesion count and IGA.
- Record any SAEs related to study medication.
- At Visits 10, 11, 12, and 13, schedule the next study visit.
- If an acne flare occurs during the PTP, the subject is to notify the site and report for an unscheduled visit at which acne severity will be assessed and treatment options will be considered. If the subject refuses to return, the investigator is to attempt to determine the acne severity and type of retreatment through discussion with the subject and with the subject's prescribing physician.

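### The protocol gives conflicting rules for recording adverse events at Visit 9, and the post-treatment safety endpoint names physical examinations that no post-treatment visit schedules

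*Combined protocol and SAP*

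**What the plan says.** Section 4.2.2.2 and the synopsis give the same secondary safety endpoint for the PTP: "Safety as assessed through the monitoring of AEs, laboratory test results, vital signs, and physical examinations".

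On adverse events at Visit 9, the text points two ways:

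- Section 7.2.6, the procedure list for Visit 9, says "Record any AEs". Section 7.2.7, covering Visits 10 to 14, changes the instruction to "Record any SAEs related to study medication".
- The synopsis, under safety evaluation criteria, says "During the PTP: Serious AEs related to study drug". Footnote c to Table 1-2 says "Only serious adverse events related to study treatment will be collected"; it is attached to the adverse event row, which is marked at Visit 9 as well as at Visits 10 to 14. Section 7.4.1.1 states the same limit for the PTP and makes no exception for Visit 9.

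Section 4.1, Table 1-2 and the heading of 7.2.6 all make Visit 9 the first PTP visit. Section 7.4.4, on laboratory assessments, counts it among the visits of the active treatment period (ATP).

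On physical examinations, Table 1-2 has no such row, 7.2.6 and 7.2.7 list none, and 7.4.7 places them at Screening and at the end of treatment visit only.

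**The concern.** Visit 9 is the only visit designed to look at safety shortly after the last dose. Its own procedure list and the general PTP rule cannot both be followed: a non-serious adverse event that begins in the weeks after treatment is recorded under the first and left out under the second. Section 8.5 plans to summarize adverse events by frequency and severity, and 8.1 leaves the detail to a SAP finalized before database lock. A SAP can choose how to display data, but it cannot supply events that were never recorded. If sites followed different passages, frequencies for that period would also not be comparable from site to site.

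The physical examination point is smaller. An endpoint component that no visit collects cannot be reported, and the clinical study report would have to explain its absence.

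**Working it through.** No hypothesis test, power or sample-size figure is involved, so the check is a comparison of the text and a count against Table 1-2.

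**Adverse event rule at Visit 9**

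| Place | What it collects at Visit 9 |
|---|---|
| 7.2.6 (Visit 9 procedures) | any adverse event |
| Synopsis, safety evaluation criteria | related serious events only (whole PTP) |
| Table 1-2, footnote c | related serious events only (row marked at Visit 9) |
| 7.4.1.1 | related serious events only (whole PTP) |

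The count is 1 place against 3. Section 7.2.7 does not settle it, because it covers only Visits 10 to 14. The change of wording between 7.2.6 and 7.2.7 does suggest that fuller recording at Visit 9 was intended.

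**Period affected**

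Visit 8 is at Week 20 and Visit 9 at Week 24: 24 − 20 = 4 weeks, or 4 × 7 = 28 days. Each visit has a window of ±4 days.

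- If both windows apply around the nominal weeks, the interval runs from 28 − (4 + 4) = 20 days to 28 + (4 + 4) = 36 days.
- If Visit 9 is timed from the actual end of treatment visit, as 4.1 can be read, it runs from 28 − 4 = 24 days to 28 + 4 = 32 days.

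Either way it is about 4 weeks. The documents give no adverse event rate for this period, so the number of events at stake cannot be estimated from them.

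**Endpoint components against the PTP schedule**

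The PTP has 6 scheduled visits (Visits 9 to 14).

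| Component of the endpoint | Scheduled PTP visits |
|---|---|
| Adverse events | 6 of 6, under the disputed rule |
| Laboratory tests | 1 of 6 (Visit 9) |
| Vital signs | 1 of 6 (Visit 9) |
| Physical examination | 0 of 6 |

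Early withdrawal does not supply the missing examination. Sections 5.4 and 7.2.8 send subjects who leave during the PTP through the end-of-study procedures, and the Visit 14/EOS column of Table 1-2 contains no examination. The last scheduled examination is therefore at Visit 8, which belongs to the ATP.

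Two details: 7.4.4 also permits as-needed repeats of laboratory tests that were abnormal at end of treatment, and 7.4.6 omits the Visit 9 vital signs that Table 1-2 and 7.2.6 both schedule.

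**The case against.** The best defence on Visit 9 is that the intention can be worked out. The visit is titled a post-treatment safety visit, 7.4.4 groups it with the ATP visits, and only from Visit 10 do the procedures switch to related serious events. On that reading the PTP restriction was meant for the later visits. This is plausible, and it supports the direction of the fix, but it does not remove the conflict. Footnote c sits on a row marked at Visit 9, and 4.1, Table 1-2 and the 7.2.6 heading put that visit in the PTP. Section 7.4.4 is one more passage to align.

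It can also be said that the endpoint bullet fixes no time points, and that its wording matches the general safety sentence in 3.1, under the ATP objective, so it looks carried over. That is fair. A reader might infer that the whole endpoint cannot be produced; it can, in three of its four components. Only the physical examination lacks a PTP source, and removing it loses no data.

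A reader might also infer that sites did record different things. The documents do not show this. The study uses one study-specific eCRF and a monitoring plan, neither of which is available, and a common form could have imposed one practice. Divergence is possible, not established. Even a uniform practice, however, would depart from some part of the protocol, and the restrictive one would lose events.

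Finally, a reader might see a further contradiction between collecting only related serious events in the PTP and requiring every serious event to be reported to the sponsor (7.4.1.4, 7.4.2, 13.2.1 and 13.2.2). The documents do not support calling that an error. The collection rule in 7.4.1.1 comes with the case report form's adverse event page, while the 24-hour reporting uses a separate form with its own causality assessment. The two can run side by side, unrelated serious events still reach the sponsor, and 8.5 leaves their display to the SAP.

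**Conclusion.** Two inconsistencies stand on the text.

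1. The rule for adverse events at Visit 9 is contradictory, with one place recording any event and three limiting collection to related serious events. This is the part that can affect data. If the restrictive rule is followed, non-serious events in about the 4 weeks after treatment are lost for good; if practice is mixed, frequencies for that period are not comparable. The first consequence assumes that sites, or the eCRF, apply footnote c and 7.4.1.1; the second assumes that sites differ. The documents confirm neither.
2. The PTP safety endpoint names physical examinations, scheduled at 0 of 6 PTP visits. This is a correction to the endpoint wording. Laboratory tests and vital signs do have a PTP source, at Visit 9 only.

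The scope is limited. Safety is a secondary, descriptive endpoint in a single-arm study with no planned hypothesis tests, and no primary endpoint is touched. The long-term safety objective in 3.2 can still be addressed, though more narrowly than the endpoint wording suggests. The correction should be made because it is cheap and the possible loss cannot be repaired at analysis.

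**What to change.** - Reconcile the synopsis safety line, Table 1-2 footnote c, 7.2.6, 7.4.1.1 and 7.4.4 to a single adverse event collection rule for Visit 9. Recording all adverse events through Visit 9, as 7.2.6 already provides, and starting the related-serious-event limit at Visit 10 avoids losing early post-treatment events.
- In 7.4.4, describe Visit 9 as a PTP visit, in line with 4.1, Table 1-2 and 7.2.6.
- Delete physical examinations from the PTP safety endpoint in 4.2.2.2 and in the synopsis, and state there that the laboratory tests and vital signs are those of Visit 9.
- As a minor alignment, add the Visit 9 vital signs to 7.4.6.

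The cost is a protocol amendment with the approvals in 9.1 and 12.2, possible eCRF changes and some additional adverse event entries. The eCRF is not in the documents, so the size of any change to it is unknown. No visit or test is added.

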5.0 SELECTION OF STUDY POPULATION

5.1 Subject Population

It is planned to enroll approximately 200 subjects at approximately 20 sites in the US in order to provide approximately 140 subjects who complete the ATP. An individual subject will be allowed to participate in the study one time only. A rationale for the choice of sample size is provided in [Section 8.2](#) of this protocol.

5.2 Inclusion Criteria

Subjects must meet all of the following criteria to be eligible for participation in the study:

5.2.1 General Inclusion Criteria

Subjects must meet the following mandatory inclusion criteria at the time of screening to be eligible to enter the study and must agree to conform to the requirements of the study and the iPLEDGE program.

1. Subjects must provide written informed consent, including mandatory photographic consent, on a gender-specific informed consent form (ICF), and Health Insurance Portability and Accountability Act (HIPAA) authorization prior to the performance of any study-related procedures. Because the study presents different risks with regard to pregnancy for men and women, the ICFs are different for male and female subjects.
2. Subjects will be male or non-pregnant, non-lactating female subjects age 12 to 45 years.
3. Isotretinoin is teratogenic. Female subjects are prohibited from entering the study if pregnant and they are not to become pregnant during the ATP phase of the trial and for 30 days after receiving their last dose of study drug.
4. Female subjects of childbearing potential must use 2 forms of effective contraception simultaneously for 1 month before starting Absorica® (isotretinoin), while taking Absorica®, and for 1 month after Absorica® has been stopped, unless they commit to continuous abstinence from heterosexual intercourse. Female subjects who choose abstinence will also have to wait the mandatory 30-day waiting period per the study Pregnancy Prevention Program requirements. The screening visit may be repeated for a subject if, in the opinion of the investigator, the subject requires re screening.
5. Male subjects and female subjects of non-childbearing potential must be able to satisfy all inclusion/exclusion criteria within 30 days prior to first drug administration. Female subjects of childbearing potential must meet the requirements of the iPLEDGE program.

5.2.2 Specific Inclusion Criteria

1. Severe recalcitrant nodular acne, which in the opinion of the investigator is compatible with isotretinoin treatment;
2. Five (5) or more nodule lesions on the face;

3. Treatment-naïve without any prior exposure to systemic isotretinoin or other systemic retinoids (ie, acitretin, etretinate);
4. Age between 12 and 45 years;
5. Weight between 40 and 110 kg;
6. Female subjects of childbearing potential only: Negative results from serum pregnancy tests with a sensitivity of at least 25 mIU/mL. Pregnancy tests are to be performed according to the iPLEDGE specifications.
7. Good general health as determined by the investigator based on the subject's medical history, physical examination, vital signs measurements, and laboratory test results;
8. Subjects who present with stable and controlled diabetes mellitus (Types I and II) may be included in the study. However, subjects may not have been hospitalized for any diabetes-related complications in the last 12 months, and have to have been on stable medication for the preceding 6 months.

Subjects with previously diagnosed polycystic ovarian syndrome (PCOS) can be included in the study if in the opinion of the investigator they do not have any other clinically significant abnormality (eg, metabolic syndrome or elevated lipids).

5.3 Exclusion Criteria

Subjects who fulfill any of the criteria listed below will be ineligible to participate in the study.

5.3.1 General Exclusion Criteria

1. Presence of any clinically significant physical examination finding, vital signs measurement, or abnormal laboratory value;
2. Presence of a beard or other facial hair that could interfere with the study assessments;
3. Participated in another clinical trial or received an investigational product within 3 months prior to screening;
4. History of excessive or suspected abuse of alcohol (based on the clinical judgment of the investigator), recreational drugs, and/or drugs of abuse, eg, club drugs, cocaine, ecstasy/MDMA (3,4-methylenedioxymethamphetamine), heroin, inhalants, marijuana, methamphetamine, phencyclidine (PCP), prescription medications, anabolic steroids, etc., which, in the opinion of the investigator, would interfere with participation in the study;
5. Use of prohibited or restricted prior or concomitant medications (see [Section 5.3.5](#)).

